Seizure activity is a theoretical risk of TMS. Although, single pulse TMS has not caused seizure activity in healthy volunteers, seizures have been produced by single-pulse TMS in several patients with large cerebral infarcts or other structural lesions [Fauth et al. 1992; Homberg and Netz 1989; Kandler 1990]. Epilepsy patients without gross lesions may also be at a minor degree of risk from single pulse TMS. For example, in a series of studies by Hufnagel and colleagues, single-pulse TMS was occasionally able to induce seizures or activate epileptic electroencephalography (EEG) foci [Hufnagel et al. 1990a; Hufnagel et al. 1990c]. In this study slow frequency trains of stimulation were used. In the current study we propose to use single pulse stimuli with a variable interstimulus interval. However, these results may not apply in patients in whom epilepsy is medically controlled. To wit, Tassinari et al [Tassinari et al. 1990] found that TMS did not incite seizure activity in a cohort of patients receiving anti-epileptic therapy. Subjects with a personal history of epilepsy will be excluded from this study.

rTMS has been reported to cause seizures in at least 7 individuals in whom frequencies of 3Hz or higher have been utilized [Wassermann 1996].

In the clinical trials investigating the efficacy and safety of rTMS paradigms similar to the one used by the NBT in the patients with stroke, no seizures have been reported in the 27 studies in 2598 patients with stroke in 2005-2016 (Boggio 2006 Mally J and Dinya E,2008, Dafotakis M 2008, Fregni F 2006, Khedr EM 2008, Kirton A 2008, Liepert J 2007, Mansur CG 2005, Nowak DA 2008, Takeuchi N 2005, Takeuchi N 2008(a), Takeuchi N 2008(b), Khedr EM 2009, Emara T, 2010, Kakuda W 2011 (a), Kakuda W 2011 (b), Thielig S 2011, Kakuda W

2011 (c), Kakuda W 2012, Sung W 2013, Abo M 2013, Higgins 2013, Kim, 2014. Rose 2014 Cha H 2015, Zheng C 2015, Kakuda W 2016).

Further, no seizures have occurred in the studies where NBS-guided rTMS has been used (a total of 365 rTMS sessions in 25 patients with stroke) [Bashir S 2010 (b), Harvey RL, 2013, Harvey, RL, manuscript in preparation]. Similarly, no seizures occurred in the NICHE multicentre trial in the 3448 therapy sessions performed in 199 patients using the same trial device and protocol as the present trial.

Auditory Changes

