4.2. SUBJECT SELECTION CRITERIA

Candidates for this study must meet ALL of the following inclusion criteria and NONE of the exclusion criteria:

Inclusion Criteria :

- ≥ 18 years of age
- An ischemic stroke suffered 3-12 months prior to the study;
- no other known brain abnormalities by history;
- A one-sided stroke resulting in upper extremity paresis
- A Chedoke–McMaster Stroke Assessment arm stage and hand stage of 3-6 for the affected limb

Exclusion Criteria

- Implanted metallic parts of implanted electronic devices, including pacemakers, defibrillators, or implant medication pump;
- Pregnant or trying to become pregnant; Lack of pregnancy established in females of child-bearing potential by a negative urine pregnancy test at screening.
- Active alcohol abuse, illicit drug use or drug abuse or significant mental illness
- Patients suffering from depression as measured by a score of ≥ 10 on the Patient Health Questionnaire (PHQ9). For clarity, patients diagnosed with depression which is controlled with stable anti-depressive medication and in whom PHQ9 is <10 are eligible to participate in the trial.
- History of epilepsy, defined as at least two unprovoked seizures occurring greater than 24 hours apart or diagnosis of an epilepsy syndrome, and no seizures within the last 12 months.
- Any condition that would prevent the subject from giving voluntary informed consent;
- An implanted brain stimulator;
- Any metal in head with the exception of dental work or any ferromagnetic metal elsewhere in the body ;
- Enrolled or plans to enroll in an interventional trial during this study;
- Scalp wounds or infections;

- Claustrophobia precluding MRI;
- A fixed contraction deformity in the affected limb that would prevent normal dexterity if patient were neurologically intact;
- Excessive spasticity as indicated by the Modified Ashworth Spasticity (MAS) Scale >2/4 in either elbow flexors, wrist flexors or finger flexors of the affected limb
- previous stroke with residual deficits (TIAs not a reason for exclusion);
- premorbid (retrospective) modified Rankin Scale (mRS) score ≥ 2 of any aetiology;
- a concurrent progressive neurologic disorder, acute coronary syndrome, severe heart disease (NYHA Classification ≥ 3), or other major medical condition,
- confirmed or suspected lower-limb fracture preventing mobilization,
- patients requiring palliative care

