- patients planning to undergo any other occupational therapy during the 6 week active treatment period of the trial (see section 5.2 for study schedule) than what is provided in the study
- A recent injection of botulinium toxin to the affected upper limb in the last 3 months, or the need of an injection of botulinum toxin anytime during the study period and follow up.
- A recent injection of phenol to the affected upper limb in the last 6 months, or the need of an injection of phenol anytime during the study period and follow up.
- Ataxia as measured by a score ≥ 1 on item 7 (limb ataxia) of the NIH stroke scale.
- Severe sensory deficits as measured by a score of 2 on item 8 of the NIH stroke scale.
- Severe aphasia as measured by a score of ≥ 2 on item 9 (best language) of the NIH stroke scale.
- Severe neglect as measured by a score of 2 on item 11 (extinction and inattention) of the NIH stroke scale.
- Patients unable to comprehend or follow verbal commands
- Based on PI's or local physician's assessment patient unable to tolerate the trial procedure due to medical condition
- A Mini mental status exam (MMSE) <25.

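### The epilepsy exclusion in section 4.2 is narrowed by its closing 12-month seizure clause, so read literally it does not exclude some patients with epilepsy and a recent seizure, contrary to section 2.2

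*Combined protocol and SAP*

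**What the plan says.** Section 4.2 sets the rule for applying the lists: "Candidates for this study must meet ALL of the following inclusion criteria and NONE of the exclusion criteria". One exclusion bullet concerns epilepsy. It defines a history of epilepsy as at least two unprovoked seizures more than 24 hours apart "or diagnosis of an epilepsy syndrome, and no seizures within the last 12 months".

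Section 2.2, under seizure activity, states the protection without a time limit: "Subjects with a personal history of epilepsy will be excluded from this study". The same paragraph gives the reasoning. It says "Epilepsy patients without gross lesions may also be at a minor degree of risk from single pulse TMS", and adds that "these results may not apply in patients in whom epilepsy is medically controlled".

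No other eligibility criterion names epilepsy or seizures.

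**The concern.** In a list of exclusions, each added 'and' condition makes the exclusion harder to meet and so lets more people in. The 12-month clause is attached in exactly that way. Taken at its word, the bullet keeps out patients whose epilepsy is quiet and not those who have had a seizure recently. That runs against the reasoning in section 2.2, which treats medically controlled epilepsy as the case where the concern may not apply.

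The entry window sharpens this. Section 4.2 requires a stroke 3 to 12 months before the study, so essentially any seizure after that stroke falls within the last 12 months. On the natural reading, the bullet would not exclude a patient whose seizures began after the index stroke, even with an epilepsy diagnosis.

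At stake is an operative safety rule. Every participant has single-pulse mapping at baseline, and those in the active arm then have 18 sessions of 900 pulses at 110% of motor threshold. Five centers could also apply the bullet differently.

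**Working it through.** The plan gives no figure to reproduce; the check is of the logic of one criterion.

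**Inputs.** From the section 4.2 bullet:
- A = two or more unprovoked seizures more than 24 hours apart
- B = diagnosis of an epilepsy syndrome
- R = a seizure within the last 12 months

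From section 2.2: anyone with a history of epilepsy is excluded. Using the section 4.2 definition of epilepsy, that is A or B.

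**Readings of the bullet.**
- Reading 1 (natural): (A or B) and not R
- Reading 2 (narrower): A or (B and not R)
- Reading 3 (not literal): A or B or R. This takes the clause as a requirement for entry placed inside an exclusion.

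Reading 3 has a precedent in the same list. The pregnancy bullet also puts an entry requirement inside an exclusion: "Lack of pregnancy established in females of child-bearing potential by a negative urine pregnancy test at screening".

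**Is the patient excluded?**

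| A | B | R | Section 2.2 | Reading 1 | Reading 2 | Reading 3 |
|---|---|---|---|---|---|---|
| no | no | no | no | no | no | no |
| no | no | yes | no | no | no | yes |
| no | yes | no | yes | yes | yes | yes |
| no | yes | yes | yes | **no** | **no** | yes |
| yes | no | no | yes | yes | yes | yes |
| yes | no | yes | yes | **no** | yes | yes |
| yes | yes | no | yes | yes | yes | yes |
| yes | yes | yes | yes | **no** | yes | yes |

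**Counts.** Six rows are epilepsy profiles (A or B true), and three of those have a recent seizure.
- Section 2.2 excludes 6 of 6, and 3 of 3 with a recent seizure.
- Reading 1 excludes 3 of 6, and 0 of 3 with a recent seizure.
- Reading 2 excludes 5 of 6, and 2 of 3 with a recent seizure. It misses the patient with a syndrome diagnosis and a recent seizure but without two qualifying seizures.
- Reading 3 excludes 6 of 6, and 3 of 3 with a recent seizure. It also excludes a patient with a recent seizure and no epilepsy, whom section 2.2 does not mention.

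None of the three readings picks out the same patients as section 2.2, and both literal ones fall short of it.

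**After the change.** Deleting the clause gives A or B: 6 of 6, identical to section 2.2. Both literal readings exclude only patients who satisfy A or B, so deletion releases no one whom the literal text keeps out.

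**The case against.** The strongest case is that this is an obvious slip with little practical consequence. On Reading 3 no patient with epilepsy gets in, and the extra exclusion of other recent seizures does not contradict section 2.2, which does not claim to list every seizure-related exclusion. An investigator unsure of the bullet has section 2.2 itself, the inclusion criterion requiring no other brain abnormality, the exclusion for other major medical conditions, and the physician's judgment that a "patient unable to tolerate the trial procedure due to medical condition".

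The procedure is also described as low risk. The protocol places the 1 Hz train within consensus safety guidelines, and the rTMS seizures it cites from the safety workshop occurred at 3 Hz or higher. Stimulation targets the healthy hemisphere, and Appendix A rules out mapping the lesioned one. Sessions take place in a medical setting, and new symptoms, including seizure, are reviewed at each treatment visit. Section 2.2 reports that "no seizures occurred in the NICHE multicentre trial in the 3448 therapy sessions performed in 199 patients", and section 1.1 describes that population as otherwise identical apart from stroke type.

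Much of this stands as a limit on the likely harm, but it does not repair the rule. Reading 3 is not what the sentence says. Nor is it the only plausible intention: the clause could equally have been meant to let in controlled epilepsy, that is, to exclude (A or B) and R. That would admit all three seizure-free epilepsy profiles and again conflict with section 2.2. The fallback criteria are general or discretionary. The documents do not say that any of the 199 earlier patients had active epilepsy, so the absence of seizures there does not settle the question for this group.

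One caution is fair: if a requirement was intended, simply deleting the clause would lose it. The fix allows for that.

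**Conclusion.** The concern holds. Followed as written, the epilepsy bullet fails to exclude at least one kind of patient with epilepsy and a recent seizure (all three such profiles on the natural reading, one on the narrower) and so does not deliver the protection stated in section 2.2. This rests on the literal wording and on the rule that only a met exclusion keeps a candidate out.

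The counts are of logical profiles, not patients, and give no estimate of how many would be affected; the number may be small. Sample size, power and significance level are untouched. Correction is warranted because an operative safety criterion gives the wrong result when applied as written, not because a seizure rate has been shown.

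**What to change.** Reword the section 4.2 bullet to exclude any history of epilepsy (two or more unprovoked seizures more than 24 hours apart, or an epilepsy syndrome diagnosis) regardless of the date of the last seizure, and remove the 12-month clause from it. The sponsor's clinicians should say what the clause was meant to do. If they want recent seizures excluded whether or not epilepsy is diagnosed, add a separate bullet excluding any seizure within the last 12 months, and state the same in section 2.2.

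The cost is a protocol amendment covering one bullet and the screening form, plus a line in section 2.2 if the separate exclusion is added. The planned 60 patients are unaffected. The separate exclusion would also lose candidates with a recent seizure but no epilepsy; the documents do not allow their number to be estimated.

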4.3. INFORMED CONSENT

All potential subjects will give written informed consent prior to any study related procedures. The background of the proposed study and the benefits and risks of the procedures and study must be explained to the subject. The subject must sign the Institutional Review Board (IRB) approved informed consent document prior to participation. Failure to provide informed consent renders the subject ineligible for the study.

5.0 study procedures

5.1 BLINDING AND SHAM-CONDITION.

5.1.1. Blinding

Blinding is achieved as follows:

Study staff: only the person responsible for randomization and the person(s) administering rTMS at the study site(s) will be aware of whether the patient is receiving NBS-rTMS or sham-rTMS. Neither of these persons is allowed to discuss randomization with the patient or study staff. Neither of these persons will direct or perform task-oriented rehabilitation with the patient nor will they perform any outcome measure testing thus ensuring that these tasks are not influenced by knowledge of randomization.

All other members of the study staff will be unaware of randomization. The reason for the person administering rTMS is unblinded is that since a supra-motor threshold protocol of rTMS is delivered to the patients healthy motor cortex, this will cause muscle activation and visible muscle movement in the patients hand which the person administering rTMS can not avoid to observe. Since sham rTMS condition by definition will not lead to muscle activation the person administering the rTMS would become unblinded by observing the patient undergoing rTMS.

Patients:

Each individual patient will be blinded to randomization by the fact that (s)he has no prior experience of rTMS and therefore can't assess whether an active or sham condition rTMS (through the use of sham coil for rTMS) has been used in her treatment. Further, of the staff that the patient meets only the person administering rTMS will be aware of the randomization. Since that person will be explicitly forbidden to discuss that issue, the patient will be unable to obtain information on randomization. The effectiveness of the blinding will be assessed at the end of the study asking the patient what group they thought they were in.

5.1.2 Sham condition:

Sham condition will be delivered by using the NBT system to navigate and localize a sham TMS coil to the same position on the patients head as the active TMS coil would be located if active NBT-rTMS would be delivered. The sham coil will cause an auditory sensation and a mechanical scalp sensation similar to the active TMS coil but will not induce an intracranial electric field capable inducing neuromodulation. The sham coil will be used to deliver an rTMS train of equal frequency and length as the active coil (900 pulses at 1Hz).

The study will consist of 24 study visits with the possible addition of 5 additional visits as needed to complete outcome assessments.

5.2. VISIT SCHEDULE

The study will be performed over 24 to 29 sessions:

- 1) Visit 1(Screening visit): Baseline = 3-12 months after the stroke. The purpose of this visit is to obtain informed consent for the study (if not previously obtained) and to screen subjects for inclusion and exclusion criteria.
- 2) Visit 2: Baseline assessment. The purpose of this visit is to establish the baseline of injury, motor status and NBS parameters (Localization of cortical motor representation area of the target muscle to which therapeutic rTMS will be subsequently delivered, see appendix A). Subjects will also undergo a structural MRI. The subject will then be randomized to either rTMS or to sham treatment. The baseline visit may if necessary take place on 2 separate days.

- 3) Visits 3-20: During these visits the patient will undergo standardized task-oriented motor rehabilitation of the hand. In addition the patient will receive the rTMS therapy according to the protocol of the group she/he was randomized into during visit 1. The visits will take place during a 6 week period, three visits per week. During each week the visits will take place each on a separate day and a maximum of two visits will take place on consecutive days.
- 4) Visit 21: End of the task-oriented motor rehabilitation. The purpose of the visit is to establish the extent of recovery that has occurred during the rehabilitation. The visit will take place 5-10 days after the last rTMS/rehabilitation session and includes functional motor testing).1-2 visits may be needed to complete assessment.
- 5) Visit 22: 1month (±5 days) after the end of the rehabilitation therapy. The purpose of the visit is to determine whether any changes in motor function have occurred within 1 month of ending therapy. The assessment includes functional motor testing. 1-2 visits may be needed to complete assessment.
- 6) Visit 23: 3 months (±5 days) after end of the rehabilitation therapy. The purpose of this visit is to determine whether any changes in motor function or NBS parameters have occurred within 3 month of ending therapy. The assessment includes functional motor testing. In patients experiencing a new stroke, only the data prior to the event will be used in the analysis. 1-2 visits may be needed to complete assessment.
- 7) Visit 24: 6 months (±5 days) after end of the rehabilitation therapy. The purpose of this visit is to determine the long-term rehabilitation success. The assessment includes functional motor testing. In patients experiencing a new stroke, only the data prior to the event will be used in the analysis. 1-2 visits may be needed to complete assessment.

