6.0 ANALYSIS PLAN

The results of functional motor tests at end of rehabilitation (5-10 days post treatment) and at 1, 3 and 6 months after the end of rehabilitation will be compared to the results obtained at baseline to determine the functional recovery if any that has occurred. The results of patients randomized into separate groups will be compared to each other to determine the effect of rTMS.

The primary analysis population will be the intent-to-treat (ITT) population. In addition, a separate analysis will be conducted on the per protocol (PP) population.

Primary outcome measure for the trial is the Upper-extremity Fugl-Meyer score.

The beneficial effect of 1Hz NBS guided rTMS will be established if a statistically significantly greater proportion of patients receiving NBS-rTMS attain clinically important improvement in the primary outcome measure than patients receiving sham-rTMS between baseline and 6 months post-treatment.

The size of the treatment effect will be measured by the odds ratio parameter which is defined as

$$OR = \frac{P_{TRT} / (1 - P_{TRT})}{P_{REF} / (1 - P_{REF})}$$

where P_{TRT} and P_{REF} denote the proportion of subjects with clinically significant change from baseline in Fugl-Meyer score, in the treatment and reference groups respectively.

The null hypothesis is H_0 : OR = 1 and the two-sided alternative hypothesis is H_1 : $OR \neq 1$.

The proportion of responders in each treatment group will be summarized, along with the estimated odds ratio, the 95% confidence interval for OR, and the Wald Chi-square test p-value. The primary analysis will be performed on the ITT, and on the PP population as a sensitivity analysis.

Secondary outcome measures for the trial are ARAT test, , NIHSS, and EQ-5D.

Descriptive statistics will be summarized by treatment and visit. Absolute difference (in points) in improvement will be summarized for both treatment groups between baseline and 5-10 days and 1, 3 and 6 month follow-up visits and the treatment groups compared via a two-way ANOVA.

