6.1 POWER ANALYSIS AND BORROWING DATA FROM NICHE-TRIAL ACTIVE TRIAL ARM RESULTS

In a pilot study of 30 patients of whom 20 were randomized to active NBS-rTMS and 10 to sham-rTMS, 84% of the active NBS-rTMS group and 50% of the sham rTMS group attained clinically significant improvement of at least 5 points on the Fugl-Meyer score [Harvey RL 2009, Harvey RL, unpublished].

Similarly, in the completed multi-centre trial (NICHE-trial, NCT02089464) of 199 subjects using the same trial device but different sham coil design, 72% of subjects with ischemic stroke receiving active NBT-rTMS attained clinically significant improvement of at least 5 points on the Fugl-Meyer score [Harvey RL, manuscript in preparation] while the average expectation of NICHE trial site principal investigators of subjects improving was 36%.

Based on this data and sample size calculations utilizing significance level of 0.05 for p, we estimate that enrolling 60 patients need to be recruited to the present study to rule out the null hypothesis that there is no difference between active NBT-rTMS and sham-rTMS with 81% power. This assumption is based on the pilot study finding of 33% difference in responder rate between groups in favour of the NBS-rTMS group and 36% difference in the actual vs expected responder rate in patients with ischemic stroke in NICHE. However, since the active treatment arm of the present trial and the active trial arm of NICHE are treated in a completely identical manner (the same NBT device, same active rTMS protocol, the same standardized occupational therapy protocol as in NICHE, the same number of therapy sessions in the same schedule at the same trial sites, etc) this allows pooling of the data obtained in the NICHE active trial arm to the data obtained in the active trial arm in the present trial. As in NICHE there were 88 subjects with ischemic stroke receiving active NBT-rTMS. Combining their data with that of the present trial will lead into a trial population of approximately 118 subjects receiving active treatment (88 from NICHE + 30 from the present trial) and approximately 30 subjects receiving sham treatment (all from the present trial). The study power in this population is sufficient to rule out the null hypothesis with 96% power.

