6.3 ANALYSIS POPULATIONS

Intent-to-Treat (ITT) Population

The ITT population will consist of all randomized subjects. Subjects in the ITT population will be summarized and analyzed in the treatment group to which they were randomized, regardless of the treatment they actually received.

Per Protocol (PP) Population

The PP population will consist of all subjects who were randomized, received study treatment, and had no major protocol violations.

If a subject suffers a new stroke during the trial and the new stroke affects the motor function of the limb being treated in the study, only the outcome assessment data collected prior to the new stroke will be used for PP Population analysis. The sponsor will review the new strokes and determine if it affects the motor function of the limb.

Safety Population

The Safety population will consist of all subjects who received study treatment. Subjects in the safety population will be summarized and analyzed according to the treatment they actually received, regardless of whether or not they were randomized to receive that treatment.

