6.6.1.2 Non-Date Values

Every effort will be made to obtain the protocol-required data for all study assessments that are scheduled for each visit for all enrolled subjects. Missing values for the primary endpoint of Fugl-Meyer scores for post-baseline visits will be imputed using Last Observation Carried Forward (LOCF) for ITT analyses. Subjects with a six-month Fugl-Meyer score but no baseline score will have their six-month Fugl-Meyer score imputed backwards to serve as their missing baseline Fugl-Meyer score. Subjects with no baseline or six-month Fugl-Meyer score will have the mean baseline Fugl-Meyer score for their treatment arm imputed for both their baseline and six-month score.

These same imputation methods will be used for secondary endpoints as well.

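### Randomising at Visit 2, before the allocated stimulation starts at Visit 3, leaves the ITT analysis open to small, avoidable dilution from patients who leave untreated

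*Combined protocol and SAP*

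**What the plan says.** - **Timing of allocation.** Section 5.2 describes Visit 2 as baseline testing, MRI and mapping, and then states: "The subject will then be randomized to either rTMS or to sham treatment". The entry for Visits 3-20 in the same section puts it earlier: "In addition the patient will receive the rTMS therapy according to the protocol of the group she/he was randomized into during visit 1".
- **Windows.** For the treatment visits, 5.2 says "The visits will take place during a 6 week period, three visits per week". Visits 21 to 24 also have windows. None is given between Visit 2 and Visit 3.
- **Population.** Section 6.0: "The primary analysis population will be the intent-to-treat (ITT) population". Section 6.3: "The ITT population will consist of all randomized subjects". The per-protocol set is limited to randomised patients who "received study treatment, and had no major protocol violations", and serves as a sensitivity analysis.
- **Missing scores.** Section 6.6.1.2: "Missing values for the primary endpoint of Fugl-Meyer scores for post-baseline visits will be imputed using Last Observation Carried Forward (LOCF) for ITT analyses". Two further rules cover a missing baseline score and the case of no usable scores.
- **Replacement.** Section 4.1 allows extra recruitment to make up for losses, and 6.2 starts the final analysis when 60 patients have completed Visit 24.

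**The concern.** Treatment under the allocation begins at Visit 3, but the patient is committed to the analysis at Visit 2. The step in between is the start of 18 treatment visits in six weeks, each of about three hours (5.2, 5.2.4), with outside occupational therapy barred (5.2.6). Each treatment visit opens with a review of new medical problems; at Visit 3 that review comes after allocation.

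A patient who leaves in this gap has a baseline Fugl-Meyer score and nothing later. The patient stays in ITT, is imputed as unchanged, and fails the 5-point responder criterion. Such patients pull both responder rates towards zero and shrink the difference, although they say nothing about the device. In a trial of 60 with a stated power of 81%, there is little room for a loss that a later allocation would avoid.

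**Working it through.** **1. Does every imputation rule give zero change?** Section 6.6.1.2 does not say outright that the baseline score counts as the last observation. The result is the same on any reading:
- LOCF with only a baseline score: six-month score = baseline, change 0.
- Baseline missing, six-month score present: baseline set equal to the six-month score, change 0.
- No usable scores: the arm's mean baseline is used for both, change 0.

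A patient who leaves between Visits 2 and 3 is therefore a non-responder. Sections 4.1 and 6.2 can add patients but do not remove the leaver from ITT.

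**2. Reproduce the stated power.** Inputs from 6.1, 5.2.3 and 6.5: responder rates 84% against 50% (pilot) or 72% against 36% (NICHE active arm against investigators' expectation), 30 per arm, two-sided 0.05. Uncorrected two-proportion normal approximation, with p̄ the mean of p1 and p2:

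power = Φ{ [ (p1 − p2)·√n − 1.96·√(2·p̄·(1 − p̄)) ] / √(p1(1 − p1) + p2(1 − p2)) }

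- 84/50: (0.34 × 5.477 − 1.96 × 0.665) / 0.620 = 0.90, power 81.6%.
- 72/36: (0.36 × 5.477 − 1.96 × 0.705) / 0.657 = 0.90, power 81.5%.

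The plan states 81%. Its 96% for 118 against 30 also reproduces (96.1% and 95.9%). Both figures match with no allowance for untreated patients.

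**3. Add leavers.** Let d be the share of each arm lost between Visits 2 and 3. Each arm's rate becomes p(1 − d). The documents give no value of d, so it is assumed. With d = 1/30, one patient per arm, the rates become 81.2% against 48.3%, or 69.6% against 34.8%. If recruitment continues to 60 completers, the number randomised per arm is 30/(1 − d), which is 31.0 at d = 1/30.

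| d (assumed) | 60 randomised, 84/50 | 60 randomised, 72/36 | 60 completers, 84/50 | 60 completers, 72/36 |
|---|---|---|---|---|
| 0 | 81.6% | 81.5% | 81.6% | 81.5% |
| 1/30 | 77.4% | 78.5% | 78.8% | 79.9% |
| 5% | 75.2% | 76.9% | 77.4% | 79.0% |
| 10% | 68.7% | 72.0% | 73.4% | 76.6% |

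At d = 1/30 the odds ratio moves from 5.25 to 4.62 (84/50) or from 4.57 to 4.29 (72/36), towards 1 in both cases.

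**4. Which row is plausible?** The only indirect evidence is the NICHE session count in 2.2: 3448 sessions in 199 patients. With 18 planned each, 199 × 18 = 3582, so 3582 − 3448 = 134 were not delivered. A wholly untreated patient misses 18, and 134/18 = 7.4, so at most 7 of 199 (3.5%) had no session. That is close to 1/30 (3.3%). The bound holds only if 199 is the number randomised; if it counts treated patients, it says nothing.

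**The case against.** **Ordinary ITT practice.** Keeping every randomised patient is standard, patients in the gap are blinded and untreated, and the per-protocol analysis already leaves them out. This stands, and it is why the effect on the E-FIT-only comparison is dilution and not bias. It does not make the dilution necessary: a later allocation keeps ITT whole and avoids these cases.

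**Replacement and the likely rate.** Recruiting to 60 completers recovers part of the power, and the NICHE count points to about one leaver per arm or fewer. Both stand. The 5% and 10% rows show sensitivity and are not forecasts.

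**Appendix A.** A reader might infer that nothing at Visit 2 depends on the arm. The documents do not support that. Appendix A lists the refined motor threshold among the baseline procedures, and its therapy section describes that step after the coil for the randomised group is attached, with a separate instruction for sham patients. Its mapping section instead assigns threshold determination to the Focal Coil. Section 5.2.4 has the threshold determined at each treatment visit. These places must be reconciled before the change is made.

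**Borrowed NICHE patients.** A reader might also infer a bias in favour of active in the analysis with NICHE data, because sham comes wholly from E-FIT while 6.1 adds "88 subjects with ischemic stroke receiving active NBT-rTMS" to the active arm. Dilution could fall more on sham, but only if those 88 exclude patients who were never treated. Section 6.1 uses the same word, *receiving*, for the 30 planned E-FIT active patients, so the word does not mark a treated-only set. The borrowing method is in a separate analysis plan that is not among the documents. No bias figure can be given.

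**Partial remedy.** No outcome assessment falls between Visit 2 and Visit 21, so a patient who leaves after the first session is imputed in the same way. This stands; moving the allocation removes only the losses before treatment.

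**Conclusion.** The concern holds as a minor design point. Allocation comes one visit before the allocated stimulation starts, with no stated interval, and anyone lost in between enters the primary population as an untreated non-responder. In the E-FIT-only comparison this costs power without favouring either arm, provided losses are similar in both. With one leaver per arm the cost is about 3 to 4 percentage points if 60 are randomised, and about 2 to 3 if recruitment runs to 60 completers. The loss rate is assumed; the NICHE sessions support that level or lower only if 199 is the number randomised. Whether the analysis with NICHE data is affected unequally cannot be established from the documents.

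**What to change.** In 5.2 and 5.2.3, place randomisation at Visit 3, immediately before the allocated coil is first attached. Keep baseline Fugl-Meyer scoring and mapping at Visit 2, and keep ITT as all randomised subjects. Matching edits:
- correct the statement in 5.2 that randomisation takes place during Visit 1;
- in 6.8, treat the Visit 2 guess as a question on expectation before allocation;
- reconcile the sections of Appendix A on whether any baseline threshold step uses the randomised coil.

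The cost is protocol wording, including Appendix A, and having the person who randomises available on the first treatment day. No visit, procedure or patient is added. The change does not limit the time from baseline scoring to first treatment, and does not address losses between the first session and Visit 21.
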